Study Title: To Determine the Economic and Functional Impact of Peri-Operative Extension Assist Pneumatic Bracing for Primary Total Knee Arthroplasty (TKA) Non-Inferiority Trial

Study Sponsor:

Ongoing Care Solutions, Inc.

Project contact: [name], Vice President of Ongoing Care Solutions, Inc.

[name]

[name]

[contact] (Ph)

[contact] (F)

Principal Investigator: [name]

Regulatory Sponsor:

This study is an investigator initiated research trial. The study site will be considered its own regulatory sponsor and is responsible for internal data monitoring and any study reporting required by ClinicalTrials.gov.

Background and Significance

Knee osteoarthritis (OA) is increasing in the United States rapidly due to increased lifespan and obesity. The use of unloader bracing has been proposed as an adjunct to current treatments. While the use of an unloader brace has not been shown to be beneficial for patients with Kellgren-Lawrence grade 1 and 2 osteoarthritis [1], unloader braces have shown benefits in patients with end-stage osteoarthritis, Kellgren-Lawrence grade 3 and 4. These benefits include increased time to total knee arthroplasty (TKA) and lower number of injections [2]. Indeed, pneumatic unloader knee bracing has also been shown to increase strength and function of these patients with end-stage knee OA [3]. Typically, the next step for end-stage knee OA is a TKA where OA accounts for 94-97% of TKAs [4,5].

While bracing has been shown to be beneficial for patients with OA in terms of function and strength, whether these unloader braces are also similarly beneficial after surgery needs to be examined. Therefore we questioned whether wearing a brace that has previously been shown to increase strength and function in OA patients can also increase strength and function in patients after TKA.

The primary objective of this study is to determine the efficacy of bracing in improving function and rehabilitation prior to and after TKA.

Additional goal of the study is to assess time taken to normalized function after TKA and its impact on cost. Secondary objectives are to quantify and observe pain medication use, swelling, muscle strength and girth, and gait efficiency.

Study Design

Methods

This a randomized, standard of care controlled study.

Sample

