Potential subjects will be recruited from a pool of TKA patients presenting to Cleveland Clinic orthopedic providers at main campus that may benefit from using a knee brace.. This study aims to complete follow-up with 40 patients. 20 out of 40 patients will receive adjunct therapy using the OCSI brace. Patients will be allocated to one of these two groups via computer randomization. The PI ([name]) will be blinded to patient compliance and evaluation during data acquisition and statistical analysis. All study patients will receive standard of care therapy (pain medications, and other modalities as needed). At home physical therapy will occur at standard of care scheduled intervals. Once physical therapy begins at Cleveland Clinic, patients in both the control and brace group will receive outpatient Physical Therapy 2 times a week for two weeks, then the number of physical therapy visits will be at the discretion of the clinician.

Patient selection:

- Age: 50 or older

- Radiographic: Varus or valgus knee deformity less than 10 degrees
- BMI of 40 or less

Research Procedures

Visit 0: Potential patients will be consented during their office visit with [name]. Once consented, patients will be computer randomized into either the knee brace group or the control group. For the knee brace group, measurements will be taken during the clinic visit, an order will be written for the brace and sent to Hanger Clinic where they will be in contact with the study participant to schedule the brace fitting. The subject can start wearing the brace at this time until surgery.

Visit 1 (6 weeks prior to surgery): Participant will meet with study coordinator and complete both questionnaires and physical tests.

Visit 2 (1 week prior to surgery): Participant will meet with study coordinator and complete both questionnaires and physical tests.

Visit 3 (1 week after surgery): Participant will meet with study coordinator and complete both questionnaires and physical tests. The brace will NOT be worn until after staple removal (10 to 14 days after surgery).

Visit 4 (6 weeks after surgery): Participant will meet with study coordinator and complete both questionnaires and physical tests.

Visit 5 (12 weeks after surgery): Patient will meet with study coordinator and complete both questionnaires and physical tests. At this point, the study time points are complete and the brace no longer needs to be worn for the study.

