Descriptive statistics (mean, standard deviation, and coefficient of variation) will be used to compare the demographics between the two cohorts. Functional metrics will be compared pre- and post-surgery at 0- and 3- months. Unless otherwise indicated, all testing of statistical significance will be two-sided, and a difference resulting in a p-value of less than or equal to 0.05 will be considered statistically significant. Also, after each analysis, General Linear Models (GLM) will be used to control for possible confounders, including BMI, gender, age, and ethnicity.

Adverse Events and Data Monitoring Committee

Procedural safety will be documented in this study through patient and surgeon reported adverse events. ARs will be documented for all ceases in this study.

An unanticipated problem involving risks to participants or others is any event that (1) is unforeseen, (2) caused harm or placed a person at increased risk of harm, and (3) is related to the research procedures.

An Adverse Event (AE) is any untoward or unfavorable medical occurrence, including any abnormal sign (for example, abnormal physical exam or laboratory finding), symptoms, or disease. Adverse events can encompass both physical and psychological harms.

An Internal Adverse Event (AE) is an untoward medical occurrence, which occurs to participants in research conducted by Cleveland Clinic and/or Cleveland Clinic is the IRB of record.

External Adverse Event (AE) is an untoward medical occurrence experienced by subjects enrolled at other institutions for the same study approved at Cleveland Clinic or a different study using the same study drug/device.

A Serious Adverse Event (SAE) is any adverse experience that results in any of the following outcomes:

- Death

- A life-threatening experience
- Inpatient hospitalization or prolongation of existing hospitalization
- A persistent or significant disability/incapacity
- A congenital anomaly/birth defect
- Important medical events that may not result in death, be life-threatening, or require hospitalization may be considered a serious adverse experience when, based upon appropriate medical judgment, they may jeopardize the patient or subject and may require medical or surgical intervention to prevent one of the outcomes listed in this definition.

An Unexpected Adverse Event means any AE not previously known or included in the consent form or other risk information.

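### The analysis plan writes no brace-versus-control comparison of function: its one functional contrast is pre- versus post-surgery, names no arm, and uses a month-0 time point that matches no functional visit

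*Combined protocol and SAP*

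**What the plan says.** The primary objective, in Background and Significance, is about an effect of the brace: "The primary objective of this study is to determine the efficacy of bracing in improving function and rehabilitation prior to and after TKA". The Methods text under Study Design says: "This a randomized, standard of care controlled study". The Sample section aims for 40 patients completing follow-up, 20 of them given the brace.

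Data Analysis then consists of four statements:

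- On the two groups: "Descriptive statistics (mean, standard deviation, and coefficient of variation) will be used to compare the demographics between the two cohorts".
- On function: "Functional metrics will be compared pre- and post-surgery at 0- and 3- months".
- On testing, which is two-sided: "a difference resulting in a p-value of less than or equal to 0.05 will be considered statistically significant".
- On adjustment, after each analysis: "General Linear Models (GLM) will be used to control for possible confounders, including BMI, gender, age, and ethnicity".

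No other section says how function is compared. The title calls the study a "Primary Total Knee Arthroplasty (TKA) Non-Inferiority Trial", and no margin is given anywhere. On brace wear before surgery, Research Procedures (Visit 0) describes an order sent to the orthotic clinic, which contacts the participant "to schedule the brace fitting. The subject can start wearing the brace at this time until surgery".

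**The concern.** Both arms undergo knee replacement. A pre- to post-surgery change therefore contains the effect of surgery and recovery in every patient, and in the brace arm any effect of the brace as well. Only a comparison of the randomized arms separates the two, and that comparison is not written for function. An analyst who followed the sentence to the letter would produce no brace effect estimate.

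If the intended analysis is a between-arm comparison, three choices remain open:

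- whether the contrast is the difference at 12 weeks or the difference in change;
- which visit supplies the value at month 0;
- whether the result is judged for superiority or for non-inferiority.

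Each can alter the answer, and each could be settled after the data are seen.

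**Working it through.** The plan states no effect size, SD, correlation, power or margin, so there is no figure of its own to reproduce. The check has two parts: a comparison of the text with the visit schedule, and an illustration under assumed values.

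**1. Which visit is month 0?** Times are from Research Procedures and windows from the schedule table. The table's visit numbers differ from the text after surgery, so weeks from surgery are used here.

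| Functional assessment | Window | Nominal weeks to week 12 |
|---|---|---|
| week -6 | ±4 weeks | 12 + 6 = 18 |
| week -1 | ±1 week (weeks -2 to 0) | 12 + 1 = 13 |
| week +1 | ±1 week (weeks 0 to +2) | 12 - 1 = 11 |
| week +6 | ±2 weeks | not a candidate |
| week +12 | ±2 weeks | fits 3 months |

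No functional test is nominally at month 0, and Visit 0 has only consent and randomization marked. The three candidates differ in kind:

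- Week -6 is the first functional assessment. It follows randomization, and the documents do not say whether it comes before or after the brace is fitted.
- Week -1 follows possible pre-operative brace wear.
- Week +1 nominally precedes post-operative wear, which waits for staple removal at 10 to 14 days. It is the least natural reading, because the sentence sets pre-surgery against post-surgery.

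**2. Why the choice matters.** Suppose the arms are compared on change from week -1 to week 12. Let the true brace effect be D at week 12 and E at week -1, in SD units, with equal SDs at both visits and correlation r between them.

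- Expected between-arm difference in change = D - E.
- SD of change = sqrt(2(1 - r)) = 1.183, 1.000 and 0.775 at r = 0.3, 0.5 and 0.7.
- Power is from the two-sample t test with 20 per arm (38 df), two-sided alpha 0.05 and standardized effect (D - E)/sqrt(2(1 - r)).

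With D = 0.8:

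| Analysis | Quantity estimated | r = 0.3 | r = 0.5 | r = 0.7 |
|---|---|---|---|---|
| Change from week -1, E = 0 | 0.8 SD | 55% | 69% | 89% |
| Change from week -1, E = 0.2 | 0.6 SD | 35% | 46% | 67% |
| Change from week -1, E = 0.4 | 0.4 SD | 18% | 23% | 36% |
| Week-12 difference, unadjusted | 0.8 SD | 69% | 69% | 69% |

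For example, E = 0.4 and r = 0.5 give (0.8 - 0.4)/1.000 = 0.4 and power 23%.

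A model for week 12 with arm and the week -1 value as terms estimates about D - rE, with residual SD sqrt(1 - r²). Its approximate power (37 df) at r = 0.3, 0.5 and 0.7 is:

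- E = 0: 73%, 81% and 93%;
- E = 0.2: 67%, 70% and 81%;
- E = 0.4: 59%, 57% and 61%.

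All values of D, E and r are assumptions.

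**3. The decision rule.** The title implies non-inferiority, the objective speaks of improving function, and the test is for a two-sided difference. A p-value above 0.05 from that test would not show non-inferiority, which requires a confidence limit set against a margin.

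**The case against.** The strongest reply is that the between-arm comparison is plainly implied. The design is randomized with a standard-of-care control, and the sentence on function directly follows one that compares the two cohorts. The model that follows each analysis adjusts for gender, ethnicity and age, which do not vary, or hardly vary, within a patient over the study. They cannot confound a within-patient difference, so calling them confounders makes sense only for a comparison between groups. This stands as evidence of intent. A reader might infer that the plan excludes a brace-versus-control analysis, or that the trial cannot answer its primary objective. The documents do not support that: they leave the contrast unwritten but do not rule it out. Nor do they propose to report a pooled pre-post change as a brace effect.

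A second reply is that change scores are not generally inferior. That also stands. With no brace effect at week -1 and r = 0.7, change from week -1 has 89% power against 69% for the unadjusted week-12 difference, and adjustment for the week -1 value does better still. A smaller change-score estimate is also partly a different estimand, the increment after week -1, rather than simply lost effect. A reader who took the 18% to 36% figures as the expected loss would be reading the least favourable case shown.

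Neither reply fixes the contrast, the month-0 visit or the decision rule.

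**Conclusion.** The point holds as a defect in specification that must be corrected. From the text alone, the stated functional contrast names no arm, the only comparison written between the arms is of demographics, and month 0 matches no functional visit. Taken literally, the contrast yields no brace effect estimate for the primary objective. Taken as probably intended, it leaves open a choice among visits nominally 18, 13 or 11 weeks before week 12, and the choice between superiority and non-inferiority.

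The numerical consequence depends on how much brace benefit exists before surgery, which the documents do not give. For an assumed 0.8 SD effect at week 12, change from week -1 estimates anything from 0.8 SD (no week -1 effect) to 0.4 SD (0.4 SD already present), with power from 89% down to 18% over r = 0.3 to 0.7. These figures show that the choice of visit can change the result. They do not show that any one choice is always worse.

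**What to change.** Replace the sentence on function with:

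> Function will be compared between randomized arms (brace minus control, 95% CI, all randomized patients by assigned arm) at 12 weeks after surgery, and before surgery at 1 week prior, from a linear or repeated-measures model with randomized arm. Within-arm pre- to post-surgery change is descriptive only.

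The objective covers function both before and after surgery, so both time points are kept. Ranking them is for the sponsor, and should be done in advance.

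In addition:

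- Tie month 0 to one scheduled visit, given in weeks from surgery.
- State in advance which pre-operative value, if any, is the baseline covariate. Note that both pre-operative visits follow randomization and may reflect brace wear. Note also that adjusting for or subtracting the week -1 value moves the estimand towards the effect beyond pre-operative benefit.
- Reconcile the title with the objective and the test: either drop the non-inferiority label, or state a margin and judge it against the confidence interval.

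The cost is a change of text. It uses outcomes and visits already scheduled and adds no assessment, visit or patient. If a margin is chosen, it has to be justified.

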Chart review: At 9 months, the study team will review participant’s chart for pain medication utilization and number of physical therapy visits during the study.

	Visit 0 Office visit (scheduling surgery)	Visit 1 6 weeks prior to surgery (±4 weeks)	Visit 2 1 week prior to surgery (±1 week)	Visit 2 1 week after surgery (±1 week)	Visit 3 6 weeks after surgery (±2 weeks)	Visit 4 12 weeks after surgery (±2 weeks)	9 months After surgery (chart review)
Informed Consent	X						
Randomization	X						

Timed up and go (TUG) test		X	X	X	X	X	
Timed stair-climb test		X	X	X	X	X	
Single-limb stance time (bilateral)		X	X	X	X	X	
6 minute walk test		X	X	X	X	X	
AROM, PROM		X	X	X	X	X	
Knee Society objective score		X	X	X	X	X	
Knee Society functional Score		X	X	X	X	X	
KOOS (Jr)		X	X	X	X	X	
HSS scale		X	X	X	X	X	
Pain score on visual analog scale (rest)		X	X	X	X	X	
Pain score on visual analog scale (activity)		X	X	X	X	X	
Pain medications utilization		X	X	X	X	X	X
Number of therapy visits							X

- For this research study, we will ask you to fill out some additional physical tests will be performed. These tests include:
 - Timed up and go (TUG) test: standing up from seated position and walking to a designated line, walking back, and returning to seated position
 - Timed stair-climb test: walking up and down stairs
 - Single-limb stance time (bilateral): standing on one leg unassisted

- 6 minute walk test: distance walked in 6 minutes
- Patient reported outcomes will also be assessed using multiple validated questionnaires
 - Knee Society Score (KSS)
 - Knee Injury and Osteoarthritis Outcome Score (KOOS Jr)
 - HSS scale
 - Visual Analog Scale (Pain score)

Participant Compliance

Study participants will be given a pedometer and notebook supplied by the sponsor to record daily steps. This will be used to monitor compliance with physical therapy and the use of the brace as it is expected there should be increased activity over time.

Data Analysis

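### The 6-week post-operative visit collects the full functional battery but has no planned analysis, so the named comparison (0 and 3 months) would miss an early difference that closes by 12 weeks

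*Combined protocol and SAP*

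**What the plan says.** In the combined protocol and SAP, the Data Analysis section gives the timing of the functional analysis in one sentence: "Functional metrics will be compared pre- and post-surgery at 0- and 3- months". It then names general linear models to adjust for BMI, gender, age and ethnicity. It names no visit term, repeated-measures model or time-to-recovery method.

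Research Procedures schedules function tests 6 weeks and 1 week before surgery, and 1, 6 and 12 weeks after. For the 6-week visit it says "Visit 4 (6 weeks after surgery): Participant will meet with study coordinator and complete both questionnaires and physical tests". The schedule table confirms every functional, score and pain row at that visit, with the window "6 weeks after surgery (±2 weeks". The text numbers this visit 4 and the table numbers it 3, but the week label identifies it.

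On post-operative wear, the 1-week visit entry says "The brace will NOT be worn until after staple removal (10 to 14 days after surgery". Of the 12-week visit the text says "At this point, the study time points are complete and the brace no longer needs to be worn for the study". Visit 0 allows brace patients to wear the brace before surgery as well.

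Background and Significance sets a primary objective on function and rehabilitation before and after TKA, and adds "Additional goal of the study is to assess time taken to normalized function after TKA and its impact on cost".

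**The concern.** Time to normalized function is a question about speed of recovery. Suppose the brace hastens recovery and control patients catch up by 12 weeks. The gap would then be visible at 6 weeks and absent at 12, and a comparison at 0 and 3 months would look the same as if the brace had done nothing. The 6-week data would exist, but any result from them would be unplanned. With many measures and no named primary endpoint, an unplanned 6-week finding is open to selective reporting and carries little weight.

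**Working it through.** The plan gives no effect size, SD, power or margin for its 40 patients, so there is no stated figure to reproduce. The check has two parts.

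**1. Possible post-operative wear at each visit.** Inputs are the visit days and windows from the schedule table, and the start of wear at day 10 to 14 from Research Procedures. Possible wear = visit day minus 14 (late start) to visit day minus 10 (early start), not below zero, taking the brace as worn up to the visit.

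| Visit after surgery | Window (days) | Wear at early edge | Wear at nominal day | Wear at late edge |
|---|---|---|---|---|
| 1 week (day 7) | 0–14 | 0 | 0 | 0–4 |
| 6 weeks (day 42) | 28–56 | 14–18 | 42 − 14 = 28 to 42 − 10 = 32 | 42–46 |
| 12 weeks (day 84) | 70–98 | 56–60 | 84 − 14 = 70 to 84 − 10 = 74 | 84–88 |

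Two visits therefore follow appreciable post-operative wear. Their windows do not overlap (the latest 6-week day is 56, the earliest 12-week day is 70), so the 12-week visit cannot stand in for the early one.

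**Readings of 0 months.** If it means a pre-operative visit, 3 months is the only post-operative time analysed. If it means the 1-week visit, that visit has at most about 4 days of post-operative wear. Neither reading includes 6 weeks.

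**2. What each test could detect (illustration).** Inputs from the plan: 20 per arm, two-sided 0.05. Assumption: standardized differences d from 0 to 1.0, since the documents give none. Formula (normal approximation): power = Φ(d/√(2/20) − 1.96) + Φ(−d/√(2/20) − 1.96), with √(2/20) = 0.316.

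| d at the tested visit | Probability of rejecting |
|---|---|
| 0 | 5.0% |
| 0.2 | 9.7% |
| 0.5 | 35% |
| 0.8 | 72% |
| 1.0 | 88.5% |

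For example, at d = 0.8, 0.8/0.316 = 2.53, and Φ(2.53 − 1.96) = Φ(0.57) = 0.716. Power of 80% needs d = (1.96 + 0.842) × 0.316 = 0.886.

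The table applies to either visit. If the gap is 0.8 SD at 6 weeks, a 6-week test has 72% power. The 12-week test has 72% if the gap persists, 35% if 0.5 SD remains, 9.7% if 0.2 SD remains and 5% if none remains.

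**Multiplicity.** Two separate tests at 0.05 give a familywise error of 1 − 0.95² = 9.75% if independent. The schedule table has 11 rows of functional, score and pain measures, so a further time point could add up to 11 tests.

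**The case against.** The strongest case for the plan is that 12 weeks is a sensible landmark. It is the last functional test and the end of study wear. If 0 months means the pre-operative baseline, the plan is an ordinary baseline-to-end comparison. If the brace effect persists or grows with longer wear, 12 weeks is the better time point. All of that stands: it supports keeping 12 weeks, but it gives the 6-week data no analysis.

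Three stronger readings are tempting, and the documents do not support them.

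- A reader might infer that the plan excludes or discards the 6-week data. The sentence does not say that only 0 and 3 months will be used, and the data are collected. The supportable statement is that 6 weeks is not named as an analysis time.
- A reader might infer that the 1-week visit is a clean check before brace exposure. It precedes nearly all post-operative wear, but brace patients may wear the brace before surgery. A difference at 1 week could be a carry-over effect of pre-operative bracing.
- A reader might infer that a real brace effect will be missed. Nothing in the documents shows that the arms converge, and at 0.5 SD even a 6-week test has only about 35% power.

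It is also fair to say that mean contrasts at 6 and 12 weeks do not by themselves measure time to normalized function. That goal needs its own definition and method, which the plan lacks.

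**Conclusion.** The point holds as a gap between schedule, aims and analysis. The only functional test in the early part of post-operative wear has no planned analysis, although rehabilitation and speed of recovery are stated goals. This part rests on the documents alone and needs no assumption about effect size.

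The consequence is conditional. If the arms differ at 6 weeks and have fully converged by 12, the planned 3-month test rejects at its 5% false-positive rate whatever the earlier gap was. If the gap persists, little is lost at 12 weeks. The power figures are illustrations that assume standardized differences, 20 evaluable patients per arm and an unadjusted two-sample comparison. The change is worth making because it is cheap and uses data already scheduled, but the plan is not invalid without it.

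**What to change.** Revise the Data Analysis section as follows.

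- State which scheduled visit 0 months means.
- For each functional metric, compare the arms in one repeated-measures model with arm, visit and arm-by-visit terms. Include the 6-week and 12-week visits, and keep the pre-operative comparison (1 week before surgery) and the 1-week post-operative comparison, since the primary objective covers function before and after surgery.
- Report the 1-week contrast as one that may carry an effect of pre-operative bracing, not as a pre-exposure check.
- Name one contrast as primary, for example 12 weeks, and label the 6-week contrast as the secondary, early-recovery contrast.
- State the order of testing.

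This needs no new visits, patients or procedures. The cost is one more contrast per measure. The plan has no test order at present, so one must be written for the added contrasts to be interpretable.

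### No primary outcome, primary time point, multiplicity rule or deciding analysis is named while p≤0.05 applies to every test, so the error rate for the efficacy objective is undefined

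*Combined protocol and SAP*

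**What the plan says.** The only item labelled primary is an objective, in Background and Significance: "The primary objective of this study is to determine the efficacy of bracing in improving function and rehabilitation prior to and after TKA". No measure, visit or success criterion is attached to it.

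Study Design, Methods reads "This a randomized, standard of care controlled study", and the Sample section fixes the group size: "20 out of 40 patients will receive adjunct therapy using the OCSI brace". The title adds "Primary Total Knee Arthroplasty (TKA) Non-Inferiority Trial"; no margin is given anywhere.

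The schedule table lists 13 unranked outcome rows. Twelve are collected at five visits: 6 weeks and 1 week before surgery, and 1, 6 and 12 weeks after.

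The Data Analysis section has four relevant statements:
- The only comparison expressly between cohorts is of demographics, and it is descriptive.
- On efficacy: "Functional metrics will be compared pre- and post-surgery at 0- and 3- months". The metrics are not listed and the arms are not mentioned.
- On significance: "all testing of statistical significance will be two-sided, and a difference resulting in a p-value of less than or equal to 0.05" is the criterion unless otherwise indicated, and nothing is indicated elsewhere.
- On adjustment: "after each analysis, General Linear Models (GLM) will be used to control for possible confounders". BMI, gender, age and ethnicity are given as included items, so the list is open.

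**The concern.** A reader cannot tell from the plan which result would answer the primary objective. Several functional measures, more than one time point and two analyses of each (unadjusted and adjusted) all carry the same 0.05 criterion. Nothing says how many significant results, or which, would establish that the brace works. The outcome, time, model and success rule could therefore be settled after the p-values are known, and that cannot be credibly repaired later.

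The efficacy sentence adds a second difficulty. Read literally, it compares patients before and after surgery. Every patient in both arms has surgery, so a within-patient change would not isolate the effect of the brace.

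**Working it through.** The documents give no effect size, power, margin or trial-level error rate, so there is no stated figure to reproduce.

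**Inputs from the documents.** Two-sided 0.05 per test (Data Analysis). 20 with the brace, hence 40 − 20 = 20 controls (Sample). Four named physical tests: TUG, stair climb, single-limb stance and 6-minute walk. Nine function-related rows in the schedule: those four plus AROM/PROM, two Knee Society scores, KOOS Jr and HSS. Two named time points, 0 and 3 months.

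**Assumptions not in the documents.** No true difference between arms, normal outcomes, pooled t-tests (38 df, critical t 2.024), equal correlation between all tests, and success declared if any one test is significant in either direction.

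**Independent tests**, 1 − 0.95^k:
- k = 4: 1 − 0.8145 = 0.185
- k = 9: 1 − 0.6302 = 0.370
- k = 18 (nine rows at two times): 1 − 0.3972 = 0.603

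**Correlated tests**, by simulation (40,000 null trials per cell for 4 and 9 tests):

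| Tests | corr. 0 | 0.5 | 0.7 | 0.8 |
|---|---|---|---|---|
| 4, one time | 0.184 | 0.156 | 0.135 | 0.115 |
| 9, one time | 0.369 | 0.273 | 0.206 | 0.171 |
| 18, two times | 0.60 | about 0.40 | – | – |

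Repeat runs of the 18-test cell at correlation 0.5 gave 0.40 and 0.41.

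**Other success rules, one time point, same assumptions.**
- Only brace-favouring results count (nominal 2.5%): about 6–10% for four tests and 8–20% for nine rows.
- More than half of the outcomes must be significant: from about 0% to about 2.5% for four tests (three or more) and to about 3% for nine rows (five or more).

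**Choice of model.** For a single outcome, taking whichever of the unadjusted and adjusted results is significant gives about 6% when the covariates explain none of the outcome variance and about 8.5% when they explain half. This is the smaller part of the problem.

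**Time points.** Three months plausibly matches the 12-week visit. Month 0 matches no scheduled functional test: the nearest are 1 week before and 1 week after surgery, and Visit 0 has only consent and randomization.

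**Power of one test.** With 20 per arm, two-sided 0.05 and 80% power, the detectable difference is (1.960 + 0.842) × √(2/20) = 0.89 SD by the normal formula, or 0.91 SD by the t distribution.

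**The case against.** The strongest reply is that the plan is less empty than it looks. Time points are named, a randomized controlled design with two groups plainly implies a comparison of arms, and the per-test level is defined. All of that stands. It would be wrong to say that no time point or no comparison of arms is contemplated. What is missing is a designated primary time point and a specified between-arm contrast for any efficacy outcome.

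A second reply is that a 40-patient study without a power calculation is naturally exploratory. The document never says so: it sets out to determine efficacy, and its title claims a confirmatory framework.

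Third, the Sample section blinds the principal investigator to evaluation during data acquisition and analysis. That is weak mitigation. It does not cover other analysts, and it fixes no outcome, model or success rule. On the other side, nothing in the documents shows an intention to choose results after the fact; the point concerns what the plan leaves open.

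Finally, the choice of outcome, and of superiority over the titled non-inferiority, belongs to the investigators. That is correct, and the fix leaves both decisions with them.

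**Conclusion.** The point holds, and it should be resolved before outcome data are examined. The per-test level is 0.05; the error rate for the primary efficacy objective is undefined, and the plan as written gives no controlled test of that objective.

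If any one significant between-arm result sufficed, the false-positive rate would be about 12–19% (four physical tests) or 17–37% (nine rows) at one time point. Nine rows at two time points give about 40% at correlation 0.5 and 60% if independent. These figures rest on the assumed correlations, t-tests and success rule.

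A reader might infer that the trial's error rate is inflated to one of these values, or that they bound what the text allows. Neither follows. Stricter success rules give less than 5%. More time points, or counting measures rather than rows, give more: range of motion is active and passive and stance is bilateral, so nine rows hold at least 11 measures, and 1 − 0.95^11 = 0.43 at one time point if independent. The figures do not apply at all if the intended test is within-patient change or non-inferiority. The supported conclusion is that the rate is undefined, not that it has a particular value.

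**What to change.** Before outcome data are examined:

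1. The investigators name one functional outcome already in the schedule (for example TUG or 6-minute walk) at 12 weeks after surgery as primary. Identify the visit by week, because Research Procedures calls it Visit 5 and the schedule table Visit 4.
2. Replace the pre/post sentence with one between-arm comparison of the 12-week values at two-sided 0.05. Do not use change from a pre-surgery visit as the contrast. At Visit 0 the protocol says "The subject can start wearing the brace at this time until surgery", so brace wear may precede the first functional tests, and those values are not a clean baseline.
3. Fix one deciding model: either the unadjusted test, or the GLM with arm and a closed covariate list (BMI, gender, age, ethnicity). The other becomes a sensitivity analysis.
4. Label all other outcomes and times secondary or exploratory, report them with 95% confidence intervals, and state that they do not by themselves establish efficacy.
5. Reconcile the non-inferiority title with the objective of improving function and with the difference testing in Data Analysis. Keeping non-inferiority would require a margin, which the documents do not give.

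If the investigators prefer not to name a primary outcome, the alternative is to label all efficacy results exploratory and drop the aim of determining efficacy.

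**Cost.** The superiority route needs no extra patients, visits or data, but it does narrow the primary question. Favourable results on other outcomes, or before surgery (part of the stated objective), can no longer be claimed as confirmatory. Power does not increase: the single test still has 80% power only for a difference of about 0.91 SD.
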